Following the explanation, patients have their intake with a physical therapist. The patients able to perform training, will be prescribed a personalized exercise program and will be followed by a local physical therapist. This includes a training scheme for exercises at home (Appendix 2). They will be asked to train at home and once a week at the physical therapist, check their vital sings with the pulse oximeter and de SMM, and communicate these vital

Version number: 4

signs with the Luscii app to a call center Altide. In case of previously set limitations, this call center will contact the hospital (Appendix 3).

Home-monitored training

All eligible patients will participate in a three-to-nine-week (average of six weeks), partly supervised, home-monitored training program prior to elective AAA-repair. The second CPET measurement is planned after the training program. Training frequency during the prehabilitation will be five sessions per week including a weekly evaluation by the physical therapist. Training sessions at home are prepared and should be able to be performed without extra adjuncts (see below). Before and after home-monitored training sessions without a physical therapist, subjects communicate oxygen saturation, heartrate, blood pressure, number of steps (nS), and number of smoked cigarettes through the Luscii app. According to these measurements, automatic advises will be given through the app (Appendix 3).

To evaluate a difference after the average of six weeks, subjects visit the specialist in sports medicine a second time to perform a CPET. Depending on the performance of patients in relation to the improvement in this second CPET, a subdivision of an improved and a stable (not improved) group will be made. It is expected that improved patients will show an increase of their VO2 at VAT of 1,5 ml/kg/min or more.

Three months after surgery, monitoring is complete, and preoperative patient characteristics of the groups will be compared.

Home-monitored exercises

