2.4. Sample size calculation

A multivariable regression analysis will be performed to identify important risk factors, such as a low fitness at the beginning of the training, a low or high BMI ($20 \ge BMI \ge 31$), and a low or high age ($50y \ge age \ge 90y$)(18). With the rule of thumb requiring 10 subjects per variable, and a chance of improvement of 50% (3 variables (fitness t= 0, BMI, and age) x 10 subjects x 0,5= 60); 60 patients will be required to include. Inclusion of one hundred patients will be necessary to perform a multivariable regression analysis with three variables, assuming an exclusion rate of 20%, and a drop-out rate of 20%. Three small sample, randomized controlled trials showed higher VO2 at VAT after 3, 6, or

9 weeks of training in gastroenterological cancer patients, patients with AAA, and rectal cancer patients, respectively: of 10,1%; 18%; or 29% (Table 1)(11, 19, 20).

Version number: 4

Study	Inclusion	n	Wks	% Impro-	VO2	SD	95%CI	VO2	SD	95%CI	ΔVO2
				vement	t=0			t=1			
Berkel(19)	GE-patients	28	3	10,1	9,6	1,2	9,1 - 10,1	10,5	1,36	10 - 11,1	0,9
Barakat(11)	AAA patients	20	6	18	12,2		10,5 - 14,9	14,4		12,3 - 15,4	2,2
Loughney(20)	Rectal CA	17	9	29	11,6	3,4	9,9 - 13,3	15	4,2	12,7 - 17,3	3,4
	total	65			•						

Table 1. Three randomized controlled trials evaluating fitness after training. Wks= weeks, SD= standard deviation, GE= gastroenterological, AAA= abdominal aorta aneurysm, and CA= cancer.

These patients reached an improvement ranging from 0.9 ml/kg/min up to 3.4 ml/kg/min (assumed mean 1.5 ml/kg/min). When subdividing the group of patients into a group with increased fitness (> 1.5 ml/kg/min) and a group without increased fitness (≤ 1.5 ml/kg/min), a dichotomous outcome is reached.

The multivariable analysis will be performed with other patient specific characteristics, as well, such as comorbidities. Modifiable factors will be analyzed as well, such as dietary habits, social economic status, frailty score, and other information collected in the questionnaires.

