6. METHODS

6.1. Study parameters/endpoints

6.1.1. Main study parameter/endpoint

It is aimed to identify AAA patients who improve most from home monitored training, i.e., patients with an improvement of their VO2 at VAT. Patients with poor fitness are expected to benefit most.

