8. STATISTICAL ANALYSIS

8.1. Primary study parameter(s)

Comparison of patient characteristics between improved and non-improved patients, in relation to VO2 at VAT, will be done using a multivariable analysis. Data will be presented as mean and standard deviation or as median and interquartile range, as appropriate.

Categorical data will be summarized by frequency and percentage within each cohort. The comparison of improved and non-improved patients will be done with an multivariable regression analysis.

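### The primary analysis cuts the change in VO2 at VAT to improved or not improved at 1.5 ml/kg/min, which loses over a third of the information, and the responder definition varies between sections

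*Protocol*

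**What the plan says.** - **Protocol 2.4 (Sample size calculation)** divides patients into "a group with increased fitness (> 1.5 ml/kg/min) and a group without increased fitness (≤ 1.5 ml/kg/min), a dichotomous outcome is reached". The 1.5 is described as an assumed mean of improvements that range from 0.9 to 3.4 ml/kg/min in three cited trials (Table 1).
- **Protocol 8.1 (Primary study parameter)** fixes the use of the two groups: "The comparison of improved and non-improved patients will be done with an multivariable regression analysis".
- **Protocol, Objectives** sets patients who gain more than 1.5 ml/kg/min against patients who do not improve.
- **Protocol 1 (Study design, Home-monitored training)** expects improved patients to show "an increase of their VO2 at VAT of 1,5 ml/kg/min or more" and calls the others stable.
- **Protocol 6.1.1 (Main study parameter/endpoint)** speaks of "patients with an improvement of their VO2 at VAT" and gives no number.
- **Protocol 2.4** sizes the study from the binary outcome: "3 variables (fitness t= 0, BMI, and age) x 10 subjects x 0,5= 60", so that "60 patients will be required to include". This becomes 100 after 20% exclusion and 20% drop-out.
- **Protocol 8.2** analyses VO2 at VAT as a continuous measure, but as a secondary question about the average before-after difference.

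**The concern.** The main purpose is to find which characteristics go with a better response, in about 60 evaluable patients. With a split at 1.5, a gain of 1.4 counts the same as a decline, and a gain of 1.6 the same as a gain of 5. If the discarded detail carries much of the information, real predictors are more easily missed. The dependence on the smaller group, and with it the 10-per-variable rule, also comes only from the split.

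Separately, if sections do not agree on who is a responder, the primary comparison can be built in more than one way from the same data.

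**Working it through.** **1. The plan's own figures.** 3 predictors × 10 per variable ÷ 0.5 = 60, and 60 ÷ (1 − 0.20 − 0.20) = 100. Both reproduce. The formula as printed multiplies by 0.5, which would give 15; the 60 needs division.

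**2. The cut-off.** Table 1 lists gains of 0.9 (n = 28), 2.2 (n = 20) and 3.4 (n = 17).
- Unweighted: (0.9 + 2.2 + 3.4) ÷ 3 = 2.17.
- Weighted: (28 × 0.9 + 20 × 2.2 + 17 × 3.4) ÷ 65 = 127 ÷ 65 = 1.95.

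Neither is 1.5. The protocol gives no SD of the change. Assuming a normal change with SD 1 to 3, means of 1.95 to 2.17 put 56% to 75% of patients above 1.5, not 50%. At 75%, 60 patients leave 60 × 0.25 = 15 non-improvers, or 5 per variable against the plan's rule of 10.

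**3. Information kept.** For a normal outcome cut at c with proportion p on one side, the asymptotic efficiency is φ(c)² ÷ [p(1 − p)].

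| Split | Efficiency | 60 patients work like |
|---|---|---|
| 50/50 | 63.7% (= 2/π) | 38 |
| 40/60 | 62.2% | 37 |
| 30/70 | 57.6% | 35 |

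The even split is the best case. To match 60 patients analysed on the continuous scale, 60 ÷ 0.637 = 94 would be needed.

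**4. Power at n = 60.** Simulation with 3,000 runs per setting: three independent normal predictors, one with correlation r to the change and two null, a 50/50 split and two-sided 5%. Logistic regression is taken as the natural model for two groups. The r values are assumptions.

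| r | Linear | Logistic (Wald / likelihood ratio) |
|---|---|---|
| 0.30 | 63% | 43% / 46% |
| 0.35 | 78% | 56% / 61% |
| 0.40 | 88% | 69% / 73% |

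The linear column agrees with Φ(√(60 − 5) × atanh(r) − 1.96), which gives 63%, 77% and 88%. The loss is about 15 to 22 points.

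**5. Baseline fitness.** Regressing post on baseline with slope b is the same as regressing change on baseline with slope b − 1, so no link between fitness and response means b = 1, not b = 0. Error in the first test enters both baseline and change. With no true link, the induced correlation is −σ² ÷ (baseline SD × change SD), where σ is the test-error SD. The example assumes σ = 1.0 and change SD 2.0, with n = 60.

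| Baseline SD | Induced correlation | Expected b | Falsely flagged, linear | Falsely flagged, logistic |
|---|---|---|---|---|
| 3.4 (Table 1) | −0.15 | 0.91 | 20% | 14% |
| 2.0 (assumed) | −0.25 | 0.75 | 48% | 32% |
| 1.2 (Table 1) | −0.42 | 0.31 | 90% | 72% |

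Repeat runs differ by about two points. The last row is extreme, since error would make up 1.0² ÷ 1.2² = 69% of the baseline variance. Both models are affected, so part of the apparent power gain for baseline fitness is power to detect an artefact.

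**6. Responder wording.** A gain between 0 and 1.5 belongs to neither group as the Objectives describe them. It is not improved in 2.4, and it is undetermined in 6.1.1. Section 1 differs from 2.4 only at exactly 1.5.

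**The case against.** - **The objective is a responder question.** The Summary and Objectives ask to separate those who benefit from those who do not, and an effect per unit answers something different. This stands in part, and it is why the responder split should remain as a secondary analysis. But the Introduction and 6.1.1 also ask who benefits most, which is a graded question.
- **The continuous data are not discarded.** Section 8.2 uses them in a paired test and mixed models. That is correct, but those analyses address average change and do not clearly model the three predictors.
- **A reader might infer three rival thresholds, with 6.1.1 meaning any gain at all.** The document does not support this. Section 6.1.1 simply gives no number, and more than 1.5 against 1.5 or more is a minor mismatch.
- **A reader might infer that the study is shown to be underpowered.** It is not. The protocol states no target power, calls the study a pilot and gives no predictor effect sizes. The loss is relative.
- **A reader might infer that test error puts a known share of unchanged patients in the improved group.** No test-error SD is given, so no such share can be fixed. An assumed 1.3 would even exceed the baseline SD of 1.2 in the first row of Table 1.
- **A linear model does not cure everything.** Working step 5 shows that its gain for baseline fitness cannot be taken at face value. This stands and changes the remedy.

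**Conclusion.** The concern holds for the efficiency loss, the weak basis of the cut-off and the unsettled responder definition. The split gives up at least 36% of the information if the change is roughly normal; a heavy-tailed change would lose less. With 60 evaluable patients and assumed correlations of 0.30 to 0.40, that costs about 15 to 22 points of power for one predictor. The gain from a linear analysis is cleanest for age and BMI, as far as these are only weakly related to baseline fitness. It is not clean for baseline fitness itself. Among the wording differences, the ones that matter are the undefined 0 to 1.5 range in the Objectives and the missing threshold in 6.1.1. The change is worth making, since both exercise tests are already planned.

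**What to change.** 1. In 2.4 and 8.1, make the primary analysis a linear regression of post-training VO2 at VAT on baseline VO2 at VAT, age and BMI, all kept continuous. Section 2.4 speaks of low or high BMI and age; if a curved relation is expected, a curve term can carry it without categories.
2. Keep one responder split as a secondary, descriptive analysis. Word it identically in the Objectives, section 1, 2.4 and 6.1.1, state where gains from 0 to 1.5 fall, and give a reason for the cut-off.
3. State in 8.1 that regression to the mean affects the baseline-fitness coefficient under the linear and the binary model alike. It should be compared with 1 rather than 0, and either corrected for test error or interpreted with that limit, not read directly as a training response.
4. Replace the 10-per-variable rationale in 2.4, which rests on the binary outcome, and correct the printed formula if it is kept.

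**Cost.** No new data, visits or patients, but more than a single edit: the Objectives, section 1, 2.4, 6.1.1 and 8.1 all need matching text. The headline becomes an effect per unit rather than a responder table, which remains available as secondary.

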Primary Objective: To compare patient characteristics between patients with clear improvement (more than 1.5 ml/kg/min improvement in the VO2 at VAT) after a three-to-nine-week training program, with patient characteristics of those who do not improve after training We aim to identify three factors that predict responsiveness to improve preoperative aerobic fitness following the training program.

Secondary objective: To evaluate the preliminary effectiveness of an, on average, six-week home-monitored training program, in patients with AAA scheduled for elective AAA-repair to improve the preoperative VO2 at the ventilatory anaerobic threshold (VAT).

Other Secondary Objective(s):

Other secondary aims are to evaluate the feasibility of this three-to-nine-week homemonitored training program. A fall-out of some patients is expected because physical exercise requires perseverance and endeavor. This feasibility is evaluated with:

- recruitment rate (how many patients will consent to participate in relation to the patients refusing participation).
- adherence rate (how many patients will endure participation in relation to the patients who give up participation, a.k.a. dropout rate) (Appendix 1).
- completion rate (how many patients will complete participation in relation to the number of patients ending participation).
- drop-out rate (how many patients will drop out of participation in relation to the number of patients completing participation).
- Attrition rate (how many patients will ask if a transfer to another treatment facility is possible, a.k.a. churn rate).

Additionally, the individual (preliminary) effect of prehabilitation on other CPET variables will be evaluated, such as VO₂ at peak exercise (VO_{2peak}) and the oxygen uptake efficiency slope, individual response profiles on the progression in aerobic fitness, improvement of the steep ramp test throughout the program. (Appendix 2).

The postoperative course in patients after AAA repair will be described as well, by collecting data on the surgical intervention and postoperative outcomes (e.g., hospital length of stay (HLOS), number of complications, mortality rate, readmission rate).

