6.2. Randomisation, blinding and treatment allocation

It is not intended to perform randomization in this single-arm intervention study. Included subjects will be followed during their preparation before an AAA repair. These findings will be compared between patients with and without improvement after training (age, ASA, smoking, hypertension, dyslipidemia, diabetes, et cetera).

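### Section 2.4 sizes the trial for a three-variable model, then opens the same multivariable analysis to further characteristics without adding patients or calling it exploratory

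*Protocol*

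**What the plan says.** Protocol section 2.4 gives the basis for the sample size: "With the rule of thumb requiring 10 subjects per variable, and a chance of improvement of 50" per cent, applied as "3 variables (fitness t= 0, BMI, and age) x 10 subjects x 0,5= 60); 60 patients will be required to include". It then inflates for losses, "assuming an exclusion rate of 20%, and a drop-out rate of 20" per cent, and ties the resulting total to one model: "Inclusion of one hundred patients will be necessary to perform a multivariable regression analysis with three variables".

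The last paragraph of the same section widens the analysis: "The multivariable analysis will be performed with other patient specific characteristics, as well, such as comorbidities". A further sentence says that modifiable factors (diet, socio-economic status, frailty and other questionnaire data) will also be analysed. It names no model for them.

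Other places bear on which variables are meant:

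- The Introduction says twice that the study is designed around three factors: initial fitness, BMI and age.
- The Primary Objective does not name them: "We aim to identify three factors that predict responsiveness to improve preoperative aerobic fitness following the training program".
- Section 6.2 has an open list for the group comparison: "These findings will be compared between patients with and without improvement after training (age, ASA, smoking, hypertension, dyslipidemia, diabetes, et cetera".
- Section 8.1 gives the primary analysis without covariates: "Comparison of patient characteristics between improved and non-improved patients, in relation to VO2 at VAT, will be done using a multivariable analysis".
- Sections 6.1.2 and 8.2 mention diet, socio-economic status and frailty again, this time under secondary parameters.

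**The concern.** A per-variable rule supports a sample size only for the number of variables it was applied to. Section 2.4 applies it to three and then describes a multivariable analysis with more, the number left open. The stated basis for 60 and 100 patients therefore does not cover the analysis that the section describes.

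What is at stake is the primary question of who benefits from training. Each added candidate thins the data per parameter, raises the chance that some characteristic looks predictive by luck, and makes the model appear to discriminate better than it does. Nothing in the protocol tells a reader of the results which predictors were pre-specified and which came from the wider search.

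**Working it through.** **Inputs.** From section 2.4: 10 per variable, 50% improving, 3 variables, 60 evaluable, 100 enrolled, 20% exclusion and 20% drop-out. From section 8.2: a 0.05 significance level. I take it as two-sided and as applying to the predictor tests too; both are assumptions.

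**Reproducing the plan's figures.**

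- The product as printed, 3 × 10 × 0.5, is 15. The stated 60 follows from division: 3 × 10 / 0.5 = 60. The rule is thus being used as 10 improved patients per variable, with 60 × 0.5 = 30 improved.
- Enrolment: 60 / (1 − 0.20 − 0.20) = 100, so the two losses are added. Taken one after the other they give 60 / (0.8 × 0.8) = 93.75, or 94.

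**More variables under the same rule.** Improved patients per variable = 30 / k. Evaluable patients needed = 10 × k / 0.5. Enrolment needed = evaluable / 0.6.

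| k | Example | Improved per variable | Evaluable needed | Enrolled needed |
|---|---|---|---|---|
| 3 | fitness, BMI, age | 10 | 60 | 100 |
| 4 | one comorbidity added | 7.5 | 80 | 134 |
| 6 | hypertension, dyslipidaemia, diabetes added | 5 | 120 | 200 |
| 8 | ASA and smoking added as well | 3.75 | 160 | 267 |

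The examples for 6 and 8 borrow names from section 6.2. The protocol does not fix the count.

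**Chance findings when no predictor has an effect.** With k independent tests at 0.05, the chance of at least one p<0.05 is 1 − 0.95^k:

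- k = 3: 1 − 0.857 = 14%
- k = 4: 1 − 0.815 = 19%
- k = 6: 1 − 0.735 = 26%
- k = 8: 1 − 0.663 = 34%

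Simulation of the full logistic model (60 patients, 30 improved, independent noise predictors) gives similar values: 11-14% at k = 3, 27% at k = 6 and 34-37% at k = 8. The apparent c-statistic from pure noise is 0.62, 0.67-0.68 and 0.70-0.71. For one true factor with an odds ratio of 2.0 per SD, the median estimate is 2.1, 2.2 and 2.3. At these counts the main cost is false predictors and optimistic discrimination, more than an inflated typical estimate.

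**Coding of BMI and age.** Section 2.4 treats both low and high values of each as risk factors, which one linear term cannot represent. With two parameters each for BMI and age and one for fitness, k = 5. Then 30 / 5 = 6 improved patients per parameter, and the rule would need 10 × 5 / 0.5 = 100 evaluable (100 / 0.6 = 167 enrolled). The three named factors alone may therefore not meet the rule.

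**The case against.** The best defence is that the protocol does name its three factors. The Introduction does so twice and section 2.4 sizes for exactly those, so the three factors of the Primary Objective are most naturally the same ones. That stands, and it makes the remedy easy. It does not remove the sentence that extends the multivariable analysis to other characteristics.

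The rule is worded as 10 subjects per variable, and 60 subjects would then allow six variables. But on that reading three variables need only 30 patients. The protocol's 60 arises only by counting improved patients.

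The protocol calls the study a pilot in sections 6.3 and 7.5 and foresees a larger trial. That lowers the severity, but identifying predictors is still the primary objective and no predictor analysis is labelled exploratory. A statistical analysis plan may also fix covariates, selection and multiplicity, so their absence from section 8.1 is no finding. Such a plan could not make section 2.4 agree with itself.

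A reader might infer something stronger: that every questionnaire item enters the same model, so that the announced predictors will mostly be noise. Counting about 21 candidates across sections 2.4, 3.1 and 6.2 and entering them together gives 30 / 21 = 1.4 improved patients per variable, a false predictor in about 80% of null simulations and an apparent c-statistic of about 0.86. The documents do not support this. Only other patient characteristics such as comorbidities are placed in the multivariable analysis. Diet, socio-economic status, frailty and questionnaire data are to be analysed with no model named, and they recur under secondary parameters. Section 6.2 lists characteristics to compare, not model terms. The count of 21 is a constructed worst case.

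**Conclusion.** The concern holds in a limited form. Section 2.4 justifies its sample size for three variables and then describes a wider multivariable analysis with no limit, no added patients and no exploratory label. The mismatch begins with the first added variable (7.5 improved patients instead of 10). At six to eight variables, the chance of at least one false predictor under the null is about 27% to 37%, against about 14% for three. These figures assume that 30 of 60 evaluable patients improve, independent predictors, one parameter per variable and testing at 0.05. The number of added variables is an assumption, because the protocol leaves it open. The point should be fixed; it is not fatal, since the three-variable analysis remains available as planned.

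**What to change.** 1. In sections 2.4 and 8.1, restrict the primary model to initial fitness, BMI and age, in line with the Introduction.
2. In the Primary Objective, speak of assessing three pre-specified factors (initial fitness, BMI and age) instead of identifying three factors.
3. Move comorbidities and all other characteristics to a separate analysis labelled exploratory and hypothesis-generating, reported as estimates with confidence intervals and no claims of significance.
4. State how BMI and age are coded. If each takes two parameters, restate the basis as 6 improved patients per parameter for 60 evaluable patients, or recompute the sample size.
5. While section 2.4 is open, print the calculation as a division by 0.5.

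A joint test of the three factors, or a penalised model for the exploratory part, is optional.

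The cost is wording only, with no new data. No extra patients are needed unless the coding takes more than one parameter per factor and the sponsor wants to keep 10 improved patients per parameter. The downside is that the other characteristics can be reported only as exploratory.
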